2.0	11APR2022	PPD	Cancellation of the final analysis after the database lock (IAP update performed after the CSR and CSR addendum deliveries in order to remove the protocol defined final data cut-off)

4 Purpose of the Integrated Analysis Plan

The purpose of this integrated analysis plan (IAP) is to document technical and detailed specifications for the analyses of data collected for bintrafusp alfa in MS200647-0008 study for CSR addendum.

Results of the analyses described in this IAP will be included in the Clinical Study Report (CSR) addendum with May 2020 cut-off. Additionally, the planned analyses identified in this IAP may be included in regulatory submissions or future manuscripts. Any post-hoc, or unplanned analyses performed to provide results for inclusion in the CSR addendum but not identified in this prospective IAP will be clearly identified in the CSR addendum.

The current analyses purpose is to provide additional data update using 15May2020 data cutoff. The analyses for the CSR were based on 24Aug2018 data cutoff. Since the last participant started on 24th August 2017, the following data will be unchanged from CSR and analyses will not be repeated:

- Demographics, medical history, others baseline characteristics and previous anticancer therapies
- Confirmed and unconfirmed Best Overall Response (BOR) by Investigator (BOR by Independent Review Committee (IRC) will be described as changes for gastric cohort have been observed) and related subgroup analysis

Following analysis will not be run using the new cutoff due to the exploratory nature of the non-safety endpoints:

- All irRECIST and mRECIST analysis
- Efficacy subgroup analysis for gastric cancer histology and PD-L1 expression in combined positive score
- Patient-reported Outcomes (PRO) analysis
- Cytokines analysis

But in the opposite, new analysis will be added and described in this IAP such as:

- Neutralizing antibody data (nAb) analysis
- ADA analysis (duration of response, time to onset, ADA titer analysis)
- Efficacy subgroup analysis by PD-L1 whole tumor and PD-L1 tumor microenvironment
- Bleeding events and anemia description
- COVID-19 analysis

5 Objectives and Endpoints

Refer to protocol version 7.

6 Overview of Planned Analyses

This IAP will address analyses used to support CSR addendum.

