14.1 Best Overall Response

Best overall response (BOR) will be assessed based on the tumor response at different evaluation time points from baseline until the first documented disease progression. The unconfirmed BOR will be defined by the best overall response reached by the participant during this period, while the confirmed BOR will have to meet additional rules of confirmation as defined in the following sections. Only tumor assessments performed before the start of any further anticancer treatment will be considered in the assessment of BOR. Clinical deterioration will not be considered as documented disease progression.

Objective Response (OR) is defined as complete response (CR) or partial response (PR) according to evaluation criteria from start date until documented disease progression. Patients who do not have an on-treatment radiographic tumor assessment due to early progression, who receive anti-tumor treatments other than the study treatments prior to reaching a CR or PR, or who die, progress, or drop out for any reason prior to reaching a CR or PR will be counted as non-responders in the assessment of OR. Each patient will have an objective response status (0: no OR; 1: OR). OR rate (ORR) is the proportion of patients with OR in the analysis set.

Disease Control Rate (DCR) is defined as the proportion of participants with BOR according to evaluation criteria of CR, PR, or SD. For RECIST 1.1 as adjudicated by IRC, non-CR/non-PD will also be considered in DCR evaluation.

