The analysis of DR will be performed using confirmed CR/PR according to RECIST 1.1 as measured by the investigator. For dose expansion participants (excluding HCC as there is no responder), analysis of DR according to RECIST 1.1 as measured by the IRC will also be performed.

DR will be censored in the following scenarios:

- Participants who do not experience an event (PD or death) will be right-censored on the date of their last evaluable (non-missing and non "Not Evaluable") tumor assessment.
- Participants who start new anti-cancer treatment prior to an event will be censored on the date of the last evaluable tumor assessment before anti-cancer therapy is given.
- Participants with an event after two or more subsequent missing response assessments (i.e. 2 times the scheduled time interval between two subsequent response assessments) will be censored on the date of the last evaluable (non-missing and non "Not Evaluable") tumor assessment.
 - Note: 2 times the scheduled time interval means 84 days during the treatment period and 168 days during the follow-up period (for participants who ended the treatment not for progression).
- Participants who do not have a baseline tumor assessment or who do not have any post-baseline tumor assessments will be censored on the date of first dose unless death occurred on or before the time of the second planned tumor assessment in which case the death will be considered an event.

 $DR = (date \ of \ PD \ or \ death/censoring - date \ of \ objective \ response + 1)/30.4375 \ (months).$

The analysis of DR will be performed with a Kaplan-Meier method (product-limit estimates) and a summary of associated statistics will be presented including corresponding two-sided 95% CIs. The CIs for the median will be calculated according to Brookmeyer and Crowley (1982) and CIs for the survival function estimates at month 3, 6, 12, 18, 24, 36, and 48 will be derived using the log-log transformation according to Kalbfleisch and Prentice (1980) (CONFTYPE=loglog default option in SAS PROC LIFETEST). The estimate of standard error will be computed using Greenwood's formula. DR rates with their CI at 3, 6, 9, 12, 18, 24, 36, and 48 months will be presented, as well as the number of participants at risk and failed.

The time and duration of response per participant will be displayed in a swimmer graph.

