15.3 Evaluation of Potential Effect of ADA/nAb on Bintrafusp alfa Efficacy

Analysis Sets: Immunogenicity analysis set

Following analysis will be described by subgroup of ADA (never positive/ever positive) and nAb (never positive [ie: no PD-L1 positive assay and no TGF β positive assay at any timepoint including baseline]/ever positive [ie either PD-L1 or TGF β positive assay at any timepoint including baseline]):

- Confirmed BOR per Investigator as described in Section 14.1.1 for dose escalation cohorts

- Confirmed BOR per Investigator and IRC as described in Section 14.1.1 and Section 14.1.2 for dose expansion cohorts
- PFS per Investigator as described in Section 14.3 for dose escalation cohorts and respective Kaplan-Meier curve
- PFS per Investigator and IRC as described in Section 14.3 for dose expansion cohorts and respective Kaplan-Meier curve
- OS as described in Section 14.4 and respective Kaplan-Meier curve
- Listings of efficacy assessments and immunology parameters for ADA positive subjects will include: cohort, participant identifier, age, sex, ADA and nAb categories, date of first study treatment, treatment duration, cBOR, PFS, time to response, DR and OS. Subjects with treatment ongoing or response ongoing will be flagged.

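### SAP section 4 carries investigator BOR forward from the 2018 cut-off for a reason that fixes only baseline data, while sections 14.2, 14.5 and 15.3 use investigator responses at the 2020 cut-off

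*SAP*

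**What the plan says.** SAP section 4 sets the two data cut-offs. For the CSR: "The analyses for the CSR were based on 24Aug2018 data cutoff". For the addendum: "The current analyses purpose is to provide additional data update using 15May2020 data cutoff". It then lists what will not be rerun, introduced by "Since the last participant started on 24th August 2017, the following data will be unchanged from CSR and analyses will not be repeated". The list has two bullets. The first covers demographics, medical history, other baseline characteristics and previous anticancer therapies. The second covers confirmed and unconfirmed investigator BOR with its related subgroup analysis. Inside that second bullet is an exception for the IRC read, which "will be described as changes for gastric cohort have been observed".

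The later sections read as follows.

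- SAP 6: all data up to the clinical cut-off are included.
- SAP 14.1: BOR is assessed "based on the tumor response at different evaluation time points from baseline until the first documented disease progression". There is no calendar limit.
- SAP 14.2: "The analysis of DR will be performed using confirmed CR/PR according to RECIST 1.1 as measured by the investigator". DR is not on the list of analyses left unrepeated.
- SAP 14.5, table of efficacy assessments by subgroup: investigator BOR is ticked for PD-L1 on tumor cells, ADA and nAb.
- SAP 15.3: by ADA and nAb status, "Confirmed BOR per Investigator and IRC as described in Section 14.1.1 and Section 14.1.2 for dose expansion cohorts", with the investigator read alone for dose escalation.

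Protocol 8.3.2 lists investigator BOR as a secondary endpoint of both parts. In dose escalation it is the only efficacy endpoint on that list, and protocol 2.2.2 has those scans read locally only.

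**The concern.** The stated reason applies to the first bullet but not to the second. Once the last participant has started, baseline data cannot change. BOR can: a participant without progression at the CSR cut-off may still move from SD to PR, from PR to CR, or from an unconfirmed to a confirmed response. Enrolment had ended for the IRC read as well, and the plan itself records that the IRC result moved in one cohort.

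What is at stake is the consistency of the addendum. An investigator ORR as of August 2018 could stand beside an investigator DR whose responders are counted as of May 2020, beside investigator subgroup response rates from 2020, and beside an updated IRC ORR. Nothing says which response set each output uses. Dose escalation is most exposed, because no IRC update covers it. No later report would correct the mismatch, since SAP 6.1 and 7 cancel the final analysis.

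**Working it through.** The plan states no figure for the length of the gap or for any change in ORR, so there is nothing to reproduce. The check is date arithmetic plus a comparison of sections.

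**Inputs.** Last start 24 Aug 2017, CSR cut-off 24 Aug 2018 and addendum cut-off 15 May 2020 (SAP 4). One month = 30.4375 days (SAP 9.5). On-treatment scans at Week 7 and then every 6 weeks in the expansion part (protocol 7.1.2.2). Scans every 12 weeks after 12 months in escalation (protocol Table 1, footnote v). Scans every 12 weeks until PD for those off treatment without progression (protocol 7.1.5.2). Confirmation at least 4 weeks after first response (SAP 14.1.1).

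**Follow-up before the CSR cut-off, last participant.** 24 Aug 2017 to 24 Aug 2018 = 365 days; 365 / 30.4375 = 11.99 months; 365 / 42 = 8.7, so about 8 six-weekly scans. Everyone else had at least as long since first dose.

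**Follow-up between the cut-offs.** 24 Aug 2018 to 15 May 2020 = 630 days; 630 / 30.4375 = 20.70 months. Scans possible for a participant without progression:

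- at 12-week intervals: 630 / 84 = 7.5, so about 7;
- at 6-week intervals: 630 / 42 = 15, an upper bound that applies only to an expansion participant still on treatment throughout.

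**Confirmation.** A PR first seen fewer than 28 days before 24 Aug 2018, that is after 27 July 2018, could only be confirmed after the CSR cut-off.

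**Size per changed response.** The documents give no response counts, so the actual change in ORR cannot be computed. As an illustration, in a cohort of 30 one added responder moves ORR by 1/30 = 3.3 percentage points. With an assumed 5 responders and Clopper-Pearson 95% limits, 5/30 = 16.7% (5.6 to 34.7) would become 6/30 = 20.0% (7.7 to 38.6).

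**Sections set against each other.**

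| Output | Section | Status at 15 May 2020 |
|---|---|---|
| Overall investigator BOR, confirmed and unconfirmed | 4 | carried forward from 2018 |
| Subgroup analysis of investigator BOR | 4 | not repeated |
| Investigator BOR by PD-L1 on tumor cells, ADA, nAb | 14.5 | planned |
| Confirmed investigator BOR by ADA/nAb | 15.3 | planned |
| DR in investigator-confirmed responders | 14.2 | planned |
| IRC BOR, ORR, DCR | 14.1.2 | planned |

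The PD-L1 tumor-cell row of 14.5 conflicts directly with section 4. Section 4 names nAb and some further ADA work as new analyses, so those rows can be read as additions. They still need an investigator response set at the new cut-off, and the plan does not say that it equals the carried-forward one.

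**The case against.** A reader might infer that investigator responses after August 2018 have been dropped, and that the end of enrolment was the sponsor's whole basis for doing so. The documents support neither inference.

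- No late investigator response is reported anywhere. By the CSR cut-off every participant had about 12 months or more since first dose, against the 6 months after last start that protocol 5.1.8 asks for. SAP 16.1.1 describes the number still on treatment at the onset of COVID-19 as low.
- Version 1.0 of the SAP is dated 29 September 2020, 137 days after the addendum cut-off, and the IRC exception rests on changes already observed. The sponsor may have compared the investigator data and found them identical. The SAP does not say so. The last-start date is therefore the only stated reason, which is not the same as the only reason.
- The gastric IRC change may have come from re-reading rather than from late responses. It shows that IRC BOR was not frozen, not that investigator BOR moved.
- A later investigator response would still be visible. It would appear in the 14.1.1 listing with confirmed BOR, the 14.1.2 efficacy listings and IRC/investigator inconsistency listing, the DR set, and the subgroup tables. The never- and ever-positive ADA groups together cover everyone with a valid ADA result.
- IRC BOR is the lead efficacy endpoint for GC, ESCC and BTC, and it is updated. Efficacy is descriptive throughout.

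All of this stands, and it limits the size of the point. It does not make the stated reason sufficient for BOR, and it does not settle which response set the DR and subgroup analyses use. That later responses would reach those outputs is exactly why they could disagree with the carried-forward table.

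**Conclusion.** The point holds as one of justification and consistency. The only reason given for carrying investigator BOR forward does not justify it, because 630 days of possible further assessment lie between the cut-offs and BOR closes only at first progression. Section 4 also conflicts with section 14.5, and it leaves the responder sets in 14.2, 14.5 and 15.3 free to differ from the overall ORR.

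The effect on any response rate is unknown and probably small. The 3.3 points per responder assumes a cohort of 30, and the count of 15 scans assumes continuous treatment on a 6-week schedule; about 7 is the figure at 12-week intervals. The conclusion needs only that some participants were free of progression at the 2018 cut-off and were scanned afterwards. The follow-up schedule allows for this, but the documents give no count. The point matters most in dose escalation, which has no IRC read to compare against.

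**What to change.** Rerun the overall investigator confirmed and unconfirmed BOR, ORR and DCR tables on the 15 May 2020 data and report any change from the CSR. Alternatively, re-derive them and state that they are identical. Use that single responder set for DR (14.2) and for the investigator analyses in 14.5 and 15.3. Amend section 4 so that what it says will not be repeated agrees with those sections, and give a reason for BOR that is separate from the one for baseline data. The IRC/investigator inconsistency listing is already planned in 14.1.2 and needs no addition.

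No new data are needed. SAP 6.1 records the addendum as approved on 25 March 2021, so the cost is a rerun of existing programs plus a short note or erratum to a delivered report.

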6.1 Decision after discontinuation of NSCLC and BTC trials

The data review outcome from the 3 randomized controlled studies in NSCLC and BTC (MS200647-0005, MS200647-0037, MS200647_0055) appears to indicate, consistently across 2 indications, either poorer observed hazard ratios for PFS and OS in the experimental arms with bintrafusp alfa or low likelihood for bintrafusp alfa to add benefits compared to standard of care. Based on this, the decision was made to not perform any final analysis after the final database lock. The study results have been described in the CSR approved on 31 March 2020 (cut-off date: 24th August 2018) and on CSR addendum approved on 25 March 2021 (cut-off date: 15th May 2020).

7 Changes to the Planned Analyses in the Clinical Study Protocol

There will be no final analysis after the final database lock.

7.1 COVID-19 Impact

No changes to the planned analysis of the efficacy endpoints will be performed due to the impact of COVID-19 outbreak.

Instead, additional outputs will be generated to assess potential impacts of COVID-19 to this study including:

- Number of participant in pre/during COVID-19 study period
- Number of COVID-19 related protocol deviations,
- Listing of participants with any missedtumor assessments, samples/procedures or missed visits due to COVID-19,
- Number of participants with Adverse Events (AEs) in pre/during COVID-19 study period, and
- Listing of AEs related to COVID-19.

8 Analysis Populations and Subgroups

8.1 Definition of Analysis Populations

Screening Analysis Set (SCR): All participants who signed the informed consent form.

Full Analysis Set (FAS) / **Safety Analysis Set (SAF):** All participants who received at least 1 dose of trial treatment (> 0 mg and/or duration of infusion > 0). The SAF terminology will be used for the safety analysis and the FAS terminology will be used for efficacy analysis.

PK Analysis Set (PKAS): All participants who complete at least 1 infusion of trial treatment, and who provide at least one post-dose sample with measurable concentration of bintrafusp alfa.

PKADA is defined as a subpopulation of the PK Analysis Set and restricted to participants who have in addition at least one valid result of antidrug antibody (ADA) at any time point.

PKNAB is defined as a subpopulation of the PK Analysis Set and restricted to participants who have in addition at least one valid result of nAb at any time point.

Immunogenicity Analysis Set (IMM): All participants who received at least 1 dose of trial drug and who have at least one valid result of ADA (i.e. ADA is negative, or positive with or without the titer result available) at any time point.

The analysis of efficacy and safety by nAb will be performed if we have nAb data for at least 5 participants.

8.2 Subgroup Definition and Parameterization

Subgroup analyses will be performed as specified in this IAP (see Section Error! Reference source not found.). All subgroup analyses will be exploratory, no adjustment for multiplicity will be performed.

For the definition of subgroup level, data as documented in the electronic case report form (eCRF) will be taken. The category "missing" will not be included in any subgroup analysis.

$\overline{\mathsf{CC}}$

The following subgroups will be defined:

- BTC classification
 - o Intrahepatic Cholangio Cell Carcinoma (CCA) / Extrahepatic CCA / Carcinoma of Vater's ampulla / Gallbladder cancer
- PD-L1 expression on tumor cells (TC), tumor microenvironment (TME) and whole tumor (WTU) at baseline
 - $0 < 1\%, \ge 1\%$
- ADA status
 - Ever positive
 - Never positive
- nAb status
 - Ever positive
 - Never positive

9 General Specifications for Data Analyses

9.1 Data Handling After Cut-off Date

Data after cut-off do not undergo the cleaning process.

Data obtained after a cut-off will not be displayed in any listings or used for summary statistics, e.g. laboratory values of samples taken after data cut-off, AE with onset date after data cut-off, etc. will not be included in any analysis or listing.

Stop dates are not affected by this rule, e.g. a stop date of AEs, which starts prior to the cut-off, but stops after the date of cut-off, will not be changed.

9.2 Definition of Baseline and Change from Baseline

The last available assessment prior to the start of study treatment is defined as the "baseline" value or "baseline" assessment for safety and efficacy analyses. If an assessment is planned to be

performed prior to the first dose of study treatment in the protocol and the assessment is performed on the same day as the first dose of study treatment, it will be assumed that it was performed prior to study treatment administration, if assessment time point is not collected or is missing. If assessment time points are collected, the observed time point will be used to determine pre-dose on study day 1 for baseline calculation. Unscheduled assessments will be used in the determination of baseline. However, if time is missing, an unscheduled assessment on study day 1 will be considered to have been obtained after study treatment administration.

Patients who start treatment and discontinue from the study on the same day may have two different sets of data collected on study day 1 (one during study and one in the End of Treatment (EOT) visit. Data reported at the EOT visit are not eligible for baseline selection.

If a scheduled pre-dose measurement actually occurred post-dose, then the corresponding measurement will be treated and analyzed similar to an unscheduled post-dose measurement.

9.3 Treatment Day

Treatment day is defined relative to the start of trial treatment. Treatment day 1 is defined as the date of first administration of trial treatment. The day before the first administration of trial treatment is defined as Treatment day -1 (there is no Treatment day 0).

9.4 Definition of Duration and 'time since' Variables

Duration (days) will be calculated by the difference of start and stop date + 1 day, if not otherwise specified. For example, survival time (days) = date of death – date of first dose of trial treatment + 1.

The time since an event (e.g. time since first diagnosis) will be calculated as reference date minus date of event. In general, the reference date will be the date of first dose of trial treatment.

9.5 Conversion Factors

Conversion of days to months or years:

The following conversion factors will be used to convert days into months or years: 1 month = 30.4375 days, 1 year = 365.25 days.

9.6 Time Window

There will be no difference between scheduled and unscheduled visits except for by-visit analyses of safety. The assignments of visit windows are described in the tables below for the purpose of by-visit analyses.

• No visit windowing will be performed at discontinuation, end of treatment, or safety follow-up visits for laboratory, vital sign, and ECG data, and post-dose assessment on Week 1 Day 1, Week 3 Day 15 visits for ECG data. Instead, the earliest non-missing observation among the unscheduled or scheduled assessments for each visit (discontinuation, end of

treatment, or safety follow-up) will be used for the analysis. For post-dose assessments on Week 1 Day 1, Week 3 Day 15 visits for ECG data, the earliest non-missing observation on Week 1 Day 1, Week 3 Day 15, respectively, will be used for the analysis.

- Scheduled and unscheduled assessments are included for visit windowing.
- If there are multiple assessments for any specified visit and some of them are from scheduled visits, the assessment from the scheduled visit with the closest distance to the planned study day will be used for analysis.
- If there are multiple assessments for any specified visit and none of them are from scheduled visits, the assessment with the closest distance to the planned study day will be used for analysis.
- If there are two or more unscheduled assessments with the same distance to the planned study day such as (-1/+1 day), the assessment prior to the planned study day such as -1 day will be used for windowing.
- There is no difference for visit windowing between tests from core serum chemistry panel and tests from the full serum chemistry panel, as those two panels will be analyzed together.
- For ECG assessment associated with study drug dose, only assessments where time points (prior to infusion or after infusion) are not missing will be considered for the analysis.

For immunogenicity analysis, unscheduled visits will also be taken into account in the analysis following the same rules as detailed above.

Table 1 Visit Window Definition for Vital Signs, Hematology, Hemostaseology, and Chemistry Assessments

From (AWLO)	To (AWHI)	Planned Study Day (AWTARGET)	Analysis Visit (N), (AVISITN)	Analysis Visit (AVISIT)
~	<1		1	Baseline
1	1	1	2	Week 1 Day 1
2	2	2	3	Week 1 Day 2*
3	11	8	4	Week 2 Day 8*
12	18	15	5	Week 3 Day 15
19	25	22	6	Week 4 Day 22
26	36	29	7	Week 5 Day 29
37	50	43	8	Week 7 Day 43
51	64	57	9	Week 9 Day 57
65	78	71	10	Week 11 Day 71
79	92	85	11	Week 13 Day 85
93	106	99	12	Week 15 Day 99
107	120	113	13	Week 17 Day 113
121	134	127	14	Week 19 Day 127

135	148	141	15	Week 21 Day 141
149#	162#	155#	16#	Week 23 Day 155#

^{*} For participants in dose expansion cohorts, there are no visits for vital signs at Week 1 Day 2 and Week 2 Day 8 and hence no visit windows for vital signs at Week 1 Day 2 and Week 2 Day 8 and the AWLO for vital sign at Week 3 Day 15 will be 2.

Time windowing should continue every 2 weeks to cover the whole data collected

